7.2 General Methodology

Data analysis will be performed by Medtronic-employed statisticians or designees. A validated statistical software package (e.g., R v4.0.0 or higher, SAS v9.4 or higher) will be used to analyze the study results.

Two formal analyses are planned for this study: one primary endpoint analysis after 28 subjects have completed the in-clinic testing and one final analysis after all subjects have completed the study. A final report will be prepared once all data collection has ended and all subjects have completed the study and have been exited.

General descriptive statistics for categorical and continuous variables will be used: categorical variables will be summarized as counts and percentages; continuous variables will be presented using mean, standard deviation, median, quartiles and range, as applicable. All confidence intervals will be presented as two-sided 95% confidence intervals, unless otherwise pre-specified.

[REDACTED]

7.3 Center Pooling

The main analyses will include data from all contributing study centers. To reduce the possibility of atypical results from a site overly influencing the study, no more than 20% of the total implanted population will be from each site unless the site gets pre-approval from Medtronic for additional enrollments.

A poolability analysis to test for difference among sites is described in the supporting analyses of the primary objective in 7.9.1.7.1. When testing for differences between sites, sites with 5 or more subjects will each be tested as separate sites. Those with less than 5 subjects will be combined into a “pooled” pseudo-site to minimize the impact of small samples on the analysis. If the pseudo-site contains more than 50% of the subjects, the sites will be combined into more than one pseudo-site. If more than one pseudo-site is needed, the sites will be randomly ordered and divided as near the midpoint as possible. If ambiguity between assigning a site to the first or second pseudo-site exists, the site will be assigned to the first pseudo-site.

7.4 Handling of Missing, Unused, and Spurious Data and Dropouts

Missing data are a potential source of bias when analyzing study data. A rigorous study design and execution will help prevent the incidence of missing data from occurring as described in Section 14.9. The analysis of the primary objective will use the first 28 subjects that complete in clinic testing and provide a primary endpoint (PAS) and if, across all subjects, more than 5% (Buhi, Goodson, & Neilands, 2008) of the average intensity scores for either the open loop (OL) or closed loop (CL) period are missing Multiple Imputation (MI) methodology for missing data will be utilized.

Prior to the use of MI, the distributions of the continuous average stimulation intensity variables will be assessed for normality (using the Shapiro-Wilk test) to determine if transformation of non-normal variables ($p \leq 0.05$) may be considered, or if a different imputation specification that is more appropriate for non-normal data may be used.

[REDACTED]
[REDACTED]
[REDACTED]
[REDACTED] Following imputation, the objective will be evaluated using MI analysis methods.

The FAS will be used for the analysis of all secondary objectives and if more than 5% of subjects have missing VAS scores at baseline or the 3-month visit then MI methodology for missing data will be utilized.

[REDACTED]
[REDACTED]
[REDACTED]
[REDACTED]

[REDACTED] [REDACTED] [REDACTED]

[REDACTED] Following imputation, the objective will be evaluated using MI analysis methods.

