14.2 Analysis Execution

The primary objective analysis will occur after 28 randomized low-back and/or leg pain subjects finish the in-clinic testing, and one final study analysis will occur after all subjects complete the study. The primary objective analysis is described in Section 14.4. A final report will be prepared once all data collection has ended and all subjects have completed the study and have been exited.

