14.4.1.6 Determination of Subjects/Data for Analysis

The analysis for this objective will follow the ITT principle by including all the low-back and/or leg pain subjects randomized for the primary analysis (PAS). If there is greater than 5% of subjects with missing values, then the subjects who are randomized but have missing average scoring of overstimulation sensation during Neuro Sense On and/or Neuro Sense Off period will be imputed using Multiple Imputation (MI). Prior to the use of MI, the distributions of the continuous variables will be assessed for normality and transformation may be considered if they are not normally distributed.

[REDACTED]

Following imputation, the objective will be evaluated using MI analysis method.

[REDACTED]

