7.1.3 Analysis Sets

- The **All Consented Set** (ACS) will include all subjects who signed the study specific ICF and enrolled in the study.
- The **Full Analysis Set** (FAS) will include all device-implanted subjects.
- The **Primary Analysis Set** (PAS) will follow the intent-to-treat (ITT) principle to include randomized low-back and leg pain subjects who will be used for the primary objective, i.e., the first 28 randomized low-back and leg pain subjects.
- The **Complete Case Set** (CCS) will include all device-implanted subjects who have data available at baseline and follow-up. This set is defined for each outcome measure at each follow-up visit. [REDACTED]

[REDACTED]

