7.9.1.2 Endpoint definition and derivation

For every overstimulation sensation brought about by protocol prescribed activities, subjects will rate the intensity of the sensation in the following 5-point Likert scale:

- No overstimulation sensation (code=0)
- Weak overstimulation sensation (code=1)
- Moderate overstimulation sensation (code=2)
- Strong overstimulation sensation (code=3)
- Very strong overstimulation sensation (code=4)

The average intensity scores during Closed Loop and Open Loop period will be calculated for each individual subject. If the average intensity score during Closed Loop period is less than that from the Open Loop period, the subject is considered as a subject with a reduction in overstimulation sensation during Closed Loop vs Open Loop period. The proportion of subjects with a reduction in overstimulation sensation among subjects who have in clinic testing need to exceed a performance goal of 50%. If there is at least one non-missing intensity score for a period, the subject’s data will be used without imputing values. If a subject is missing all intensity scores for a period, then that subject has a missing average intensity score for that period. If, across all subjects, more than 5% of the average intensity scores for the OL of CL period are missing, then MI will be utilized as specified in 7.4.

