7.9.1.6 Determination of Subjects/Data for Analysis

The primary analysis for the primary objective will follow the ITT principle by including the low-back and/or leg pain subjects randomized for the primary analysis (PAS). If more than 5% of the average intensity scores for either the OL or CL period are missing, then the subjects who are randomized but have missing average scoring of overstimulation sensation during Neuro Sense On and/or Neuro Sense Off period will be imputed using Multiple Imputation (MI) as described in 7.4.

[Redacted text block]

[Redacted text block]

[Redacted text block]

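### SAP 7.4 labels the first 28 completers as the Primary Analysis Set, while SAP 7.1.3 defines it under ITT as the first 28 randomized; the 7.4 clause should be corrected

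*SAP*

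**What the plan says.** Four places say who is analysed for the primary objective.

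- SAP 7.1.3 invokes intention to treat (ITT) and defines the Primary Analysis Set (PAS) as "i.e., the first 28 randomized low-back and leg pain subjects".
- SAP 7.9.1.6 says the primary analysis "will follow the ITT principle by including the low-back and/or leg pain subjects randomized for the primary analysis (PAS"). Randomized subjects whose average score is missing for either period are imputed if the 5% trigger is met.
- Protocol 14.4.1.6 has the same ITT and imputation text, "including all the low-back and/or leg pain subjects randomized for the primary analysis (PAS").
- SAP 7.4 says: "The analysis of the primary objective will use the first 28 subjects that complete in clinic testing and provide a primary endpoint (PAS"). The sentence goes on to prescribe multiple imputation (MI) if more than 5% of the average scores for either period are missing.

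Two further places set the timing. SAP 7.2 plans "one primary endpoint analysis after 28 subjects have completed the in-clinic testing". Protocol 14.2 says: "The primary objective analysis will occur after 28 randomized low-back and/or leg pain subjects finish the in-clinic testing".

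SAP 7.9.1.2 makes a missing average hard to produce. "If there is at least one non-missing intensity score for a period", the subject's data are used without imputation. An average is missing only when every score in that period is missing.

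**The concern.** One label carries two selection rules. Under 7.1.3, a subject who is randomized and gives no endpoint stays in the set and must be dealt with as missing. Under 7.4, that subject leaves the set and the next subject with an endpoint takes the place.

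The second rule selects on completion, which is not ITT. It also defeats the rest of its own sentence, because a set restricted to subjects with an endpoint has no missing endpoints for MI to act on.

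The primary objective is the study's only hypothesis test (Protocol 14.1.7, SAP 7.5), and with 28 subjects a single result can decide it. A programmer working from 7.4 and another working from 7.1.3 could analyse different people and reach different verdicts, each following the SAP.

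**Working it through.** **Inputs.** Null proportion 50%, alternative 80%, 28 subjects, power above 90% (Protocol Synopsis, Statistics); exact binomial test, one-sided p below 0.025 (SAP 7.9.1.5). X(n) is the number of subjects with a reduction among n.

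**1. The plan's own figure.** The cut-off is the smallest r with P(X(28) ≥ r | 0.5) < 0.025.
- r = 20: P = 0.0178, pass.
- r = 19: P = 0.0436, fail.
- Power = P(X(28) ≥ 20 | 0.8) = 0.910.

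The stated power above 90% is reproduced, so the sample size is not in question.

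**2. Missing share under each definition.**
- SAP 7.4: 0/28 by construction.
- SAP 7.1.3: one missing is 1/28 = 3.6%, below 5%; two missing is 2/28 = 7.1%, above 5%.

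These shares take the PAS as denominator. SAP 7.4 and 7.9.1.2 word the trigger as running over all subjects, which may mean a wider group. On either reading, the 7.4 set itself contains nobody to impute.

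**3. Can the verdict change?** Suppose one of the first 28 randomized has no endpoint and 19 of the other 27 show a reduction.

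| Handling | Result | One-sided p | Verdict |
|---|---|---|---|
| Test the 27 observed | 19/27 | 0.0261 | fail |
| Count the missing subject as no reduction | 19/28 | 0.0436 | fail |
| Replace by a completer with a reduction (7.4) | 20/28 | 0.0178 | pass |

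**4. How often, given exactly one missing (illustration only).** Compare replacement with counting the subject as no reduction. The latter is a comparator of convenience and is not in the visible plan. The two differ only when X(27) = 19 and the replacement is a success. If replacements resemble other completers with true rate p, the probability is P(X(27) = 19 | p) × p, where P(X(27) = 19 | p) = 2,220,075 × p^19 × (1 − p)^8.
- p = 0.6: 5.3%
- p = 0.7: 11.6%
- p = 0.8: 6.6%

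**5. Power cost of keeping the subject.** With missing counted as no reduction and a true rate of 80% among those observed, power is 0.910 with none missing and P(X(27) ≥ 20 | 0.8) = 0.844 with one.

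**The case against.** The strongest reply is that the two sets will probably be the same 28 people. Randomization takes place at the testing visit (Protocol 6), only after a clear ECAP is present (Protocol 10.15). All randomized subjects are to cross over within that testing (Protocol 10.15.4), and one score per period is enough. The higher attrition noted in the protocol's version history is not tied to this visit. This stands, and it limits how often the conflict would bite. It does not make the two definitions agree.

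SAP 7.9.1.2 and Protocol 14.4.1.2 speak of the proportion among subjects who have in-clinic testing, which leans towards completers. That describes the proportion and does not define the PAS. The timing sentences in SAP 7.2 and Protocol 14.2 do not define it either.

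Three stronger readings are tempting, and the documents do not support them.
- **An overall probability that the verdict changes.** The documents give no non-completion rate. With two or more of 28 missing, the ITT text prescribes MI on a PAS denominator, and the MI model is redacted. The gap between the SAP's two definitions therefore cannot be computed.
- **The plan has no rule for a single missing endpoint and no completer sensitivity analysis.** Parts of SAP 7.4 and the text after 7.9.1.6 are redacted. SAP 7.3 refers to "supporting analyses of the primary objective in 7.9.1.7.1", which is not visible, nor are Protocol 14.1.1 and 14.1.2. Either provision may stand there.
- **Protocol 14.4.1.6 sets a third, uncapped definition by saying all.** Its wording is qualified as those randomized for the primary analysis, and Protocol 14.8 treats the 28 as a subset of those implanted.

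**Conclusion.** The point holds as a contradiction in current, unredacted SAP text. SAP 7.1.3, SAP 7.9.1.6 and Protocol 14.4.1.6 all work from randomization; 7.4 is the outlier and is wrong as written. ITT is probably what was intended.

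The consequence is conditional. With no missing endpoint among the first 28 randomized, nothing changes. With one missing, a result of 19 successes among the other 27 fails when only those observed are tested and passes after a successful replacement. The 5.3% to 11.6% in step 4 assume exactly one missing subject, replacements that resemble other completers, and a comparator outside the visible plan. They show that the choice matters in that case and are not a forecast for this trial.

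This should be fixed because the correction is cheap and the clause governs the only test.

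**What to change.** - **SAP 7.4.** Replace the clause with wording such as: *The PAS consists of the first 28 low-back and/or leg pain subjects in order of randomization, whether or not in-clinic testing was completed; a subject without an endpoint is not replaced.*
- **SAP 7.2.** Start the primary analysis once each of these 28 has either finished or discontinued in-clinic testing.
- **MI trigger (SAP 7.4, 7.9.1.2).** State whether the 5% is counted over the PAS or over a wider group.
- **Missing endpoint below the trigger.** If the redacted text already has a rule, keep it and cross-refer. If not, fix one before the primary data are seen, so that the subject is not simply dropped.

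The cost is one SAP revision of a few sentences, with no added subjects or visits. The downside is some loss of power if a PAS endpoint is missing: for example 84.4% instead of 91.0% with one missing counted as no reduction. Power under MI cannot be stated while the model is redacted.

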7.5 Adjustments for Multiple Comparisons

Only one hypothesis test is planned for analysis of the primary objective, no adjustments for multiple endpoints are required.

7.6 Demographic and Other Baseline Characteristics

Demographic and other baseline characteristics will be summarized for the ACS, PAS, and FAS datasets. Summaries of age at baseline, sex, race, ethnicity, primary indication, primary location of pain (low back/leg, upper limb-not neck, upper-limb neck), and medical history will be included. Additionally, we will summarize the baseline outcome measures for the ACS, PAS, and FAS datasets by primary location of pain.

7.7 Treatment Characteristics

Relevant characteristics from the in-clinic testing will be summarized and described.

7.8 Interim Analyses

No Interim analysis will be performed on the primary and secondary objectives. [REDACTED]

7.9 Evaluation of Objectives

7.9.1 Primary Objective

The primary objective is to demonstrate that the proportion of low-back and leg pain subjects having a reduction in overstimulation sensation with Neuro Sense On compared to Neuro Sense Off, at the randomization and in-clinic testing visit, exceeds a performance goal of 50%.

Overstimulation is defined as an uncomfortable sensation of stimulation (intense tingling, shocking, jolting) brought about by protocol-prescribed activities [REDACTED]. This overstimulation sensation is transient and reversed by the subject returning to a neutral position.

7.9.1.1 Hypothesis

It is hypothesized that the proportion of low-back and leg pain subjects with a reduction in overstimulation sensation during Neuro Sense On compared to Neuro Sense Off period exceeds a performance goal of 50%.

$$H_0: p \leq 50\%$$

$$H_A: p > 50\%$$

7.9.1.2 Endpoint definition and derivation

For every overstimulation sensation brought about by protocol prescribed activities, subjects will rate the intensity of the sensation in the following 5-point Likert scale:

- No overstimulation sensation (code=0)
- Weak overstimulation sensation (code=1)
- Moderate overstimulation sensation (code=2)
- Strong overstimulation sensation (code=3)
- Very strong overstimulation sensation (code=4)

The average intensity scores during Closed Loop and Open Loop period will be calculated for each individual subject. If the average intensity score during Closed Loop period is less than that from the Open Loop period, the subject is considered as a subject with a reduction in overstimulation sensation during Closed Loop vs Open Loop period. The proportion of subjects with a reduction in overstimulation sensation among subjects who have in clinic testing need to exceed a performance goal of 50%. If there is at least one non-missing intensity score for a period, the subject’s data will be used without imputing values. If a subject is missing all intensity scores for a period, then that subject has a missing average intensity score for that period. If, across all subjects, more than 5% of the average intensity scores for the OL of CL period are missing, then MI will be utilized as specified in 7.4.

7.9.1.3 Performance Requirements

The null hypothesis will be rejected if the one-side 97.5% lower confidence bound is greater than 50% or, equivalently, if the p-value for the hypothesis test is less than 0.025.

7.9.1.4 Rationale for Performance Criteria

The Neuro Sense On setting is an additional feature to control overstimulation to be added to an existing device. It is expected that this feature will help majority of the subjects. The 50% performance goal is selected to ensure that majority of the low-back and/or leg pain subjects meet the criterion with 95% confidence.

7.9.1.5 Analysis Methods

The proportion of low-back and/or leg pain subjects with a reduction in overstimulation sensation during Neuro Sense On compared to Neuro Sense Off period will be calculated, with a one-sided 97.5% confidence lower bound. This proportion will be tested against 50% using a binomial exact test. The confidence lower bound needs to be greater than 50%, or equivalently, the p-value must be less than 0.025 to reject the null hypothesis.

[Redacted text block]

[Redacted text block]

7.9.1.6 Determination of Subjects/Data for Analysis

The primary analysis for the primary objective will follow the ITT principle by including the low-back and/or leg pain subjects randomized for the primary analysis (PAS). If more than 5% of the average intensity scores for either the OL or CL period are missing, then the subjects who are randomized but have missing average scoring of overstimulation sensation during Neuro Sense On and/or Neuro Sense Off period will be imputed using Multiple Imputation (MI) as described in 7.4.

[Redacted text block]

[Redacted text block]

[Redacted text block]

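### Imputation of the primary endpoint is triggered per subject in the protocol but per period in the SAP; at 28 subjects the two rules disagree when two subjects lack opposite periods

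*SAP*

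**What the plan says.** The endpoint (protocol 14.4.1.2, SAP 7.9.1.2) compares a subject's average intensity score with Neuro Sense On (closed loop, CL) with the average with Neuro Sense Off (open loop, OL). A lower On average is a success. The number of successes is tested against 50% by an exact binomial test at one-sided 0.025.

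**Trigger for imputation**
- Protocol 14.4.1.6 counts subjects: "If there is greater than 5% of subjects with missing values".
- SAP 7.9.1.6 counts period averages: "If more than 5% of the average intensity scores for either the OL or CL period are missing".
- SAP 7.9.1.2 repeats the period count: "If, across all subjects, more than 5% of the average intensity scores for the OL of CL period are missing". SAP 7.4 has the same rule.

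**What counts as missing (SAP 7.9.1.2)**
- One rating is enough to keep a period. The no-imputation rule begins "If there is at least one non-missing intensity score for a period".
- Otherwise: "If a subject is missing all intensity scores for a period, then that subject has a missing average intensity score for that period".

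**Primary Analysis Set (PAS)**
- SAP 7.1.3: "the first 28 randomized low-back and leg pain subjects".
- SAP 7.4: "The analysis of the primary objective will use the first 28 subjects that complete in clinic testing and provide a primary endpoint (PAS").
- Protocol 14.4.1.6, under the ITT principle: "including all the low-back and/or leg pain subjects randomized for the primary analysis (PAS").

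**The concern.** The endpoint belongs to the subject and is lost when either average is lost. A rule that looks at each period alone can therefore miss part of the loss, because missing values in different subjects and different periods are never added together. The protocol's count does add them. The visible SAP text gives no reason for the change of unit.

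The rule governs the primary handling of the only hypothesis test in the study. If the two documents call for different handling of the same data, someone must choose between them after the data are seen, and the choice could decide a borderline result.

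**Working it through.** **1. The plan's own figure.** Inputs from the protocol synopsis: null 50%, alternative 80%, one-sided alpha 0.025, 28 subjects, power above 90%. With X binomial(28, 0.5), P(X ≥ 19) = 0.0436 and P(X ≥ 20) = 0.0178, so 20 successes are needed. Power is P(X ≥ 20 | 0.8) = 0.910. The stated figure is reproduced.

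**2. When the triggers disagree.** Take the PAS as the first 28 randomized (SAP 7.1.3). One of 28 is 3.6% and two of 28 is 7.1%. The protocol rule therefore needs two subjects with any missing average. The SAP rule needs two missing averages in the same period.

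| Two subjects lack | Missing OL / CL | Protocol | SAP |
|---|---|---|---|
| OL; OL | 2 / 0 | impute | impute |
| CL; CL | 0 / 2 | impute | impute |
| OL; both | 2 / 1 | impute | impute |
| CL; both | 1 / 2 | impute | impute |
| both; both | 2 / 2 | impute | impute |
| OL; CL | 1 / 1 | impute | do not impute |

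With three or more such subjects, at least two must lack the same period, so both rules trigger. With one, neither does. At 28 subjects the disagreement is exactly one pattern: two subjects, one lacking only OL and the other only CL.

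**3. The SAP route in that pattern.** Assume the two subjects are left out, so n = 26. P(X ≥ 18) = 0.0378 and P(X ≥ 19) = 0.0145, so 19 are needed. The 97.5% lower bound is 48.2% at 18/26 and 52.2% at 19/26. Power at 80% is P(X ≥ 19 | 26, 0.8) = 0.869. That loss comes from having two fewer endpoints, not from the trigger itself.

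**4. The protocol route in that pattern.** The visible text gives neither the full imputation model nor the pooling rule. As an illustration, impute each of the two outcomes as a success with probability q and pool by Rubin's rules with many imputations. With s observed successes:
- pooled proportion p̂ = (s + 2q)/28
- between-imputation variance B = 2q(1 − q)/28²
- within-imputation variance U = [p̂(1 − p̂) − B]/28 (Wald) or 0.25/28 (null variance)
- z = (p̂ − 0.5)/√(U + B)

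For s = 18 and q = 18/26 = 0.692: p̂ = 19.385/28 = 0.6923 and B = 0.00054.
- Wald: U = 0.00759, z = 0.1923/0.0902 = 2.13, p = 0.0165.
- Null variance: U = 0.00893, z = 0.1923/0.0973 = 1.98, p = 0.0241.

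Both pass, where the exact test on 18/26 fails. The pass needs q of about 0.51 or more (Wald) or 0.67 or more (null variance).

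For s = 19 and q = 19/26 = 0.731, p = 0.0039 (Wald) or 0.0087 (null variance). Both pass, as does the exact test on 19/26. At q = 0, Wald still passes (0.0215) and null variance fails (0.0294). The null-variance version fails only for q below about 0.14.

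**5. How much of the 18/26 change is imputation?** The same normal approximations without imputation give z = 0.1923/√(0.6923 × 0.3077/26) = 2.12, p = 0.017 (Wald), and z = 5/√(26 × 0.25) = 1.96, p = 0.0249 (null variance). Most of the shift therefore comes from leaving the exact test, which pooling of this kind entails.

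**6. How often.** If the true rate is 80%, the chance of exactly 18/26 is 7.2% and of exactly 19/26 is 12.1%, given that the pattern in step 2 has occurred.

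**The case against.** The strongest reply is that this is a rare pattern in a rule that the SAP may refine. Both periods are tested at one visit, and a single rating keeps a period, so losing exactly one whole period in each of two subjects, in opposite periods, should be uncommon. Protocol section 14 leaves detail to the SAP. All of this stands, and it limits the size of the point. It does not explain why the SAP counts a unit that is not the endpoint's unit.

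Second, the 26-subject analysis is inferred. The visible text of neither document says what happens to a subject without an endpoint below the threshold. Text around SAP 7.4, 7.9.1.5 and 7.9.1.6 is redacted, and the protocol's section on missing data (14.1.2) cannot be read in the public copy. This stands as a condition on the result.

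Third, under SAP 7.4 the PAS contains only subjects who provide an endpoint, so neither trigger would operate. That is correct, but it conflicts with SAP 7.1.3 and with the stated ITT principle, because a randomized subject without an endpoint would be replaced by a later one.

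A reader might go further and infer that the SAP rule favours rejection, by comparing 19/26 (p = 0.0145) with 19/28 (p = 0.0436). The documents do not support this. 19/28 counts both missing subjects as failures, whereas the protocol prescribes multiple imputation, under which 19/26 still passes at plausible rates. At 18/26 the SAP route is the stricter one.

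**Conclusion.** The inconsistency is real. At 28 subjects it is confined to two subjects lacking opposite periods: 7.1% of subjects under the protocol's count against 3.6% per period under the SAP's. It would be wrong to infer that any two missing subjects are handled differently; in the other five patterns both documents impute.

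In the one divergent pattern the conclusion can change, mainly at 18/26: exact p = 0.038 without imputation, about 0.0165 or 0.024 with it. At 19/26 it changes only if the imputations are close to all failures. The net direction is not established.

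This rests on four assumptions: the first-28-randomized PAS; a complete-case analysis below the threshold; binary outcomes imputed directly, where the plan imputes period averages; and normal-theory pooling, which itself accounts for most of the change at 18/26. The figures show that the decision is sensitive to the route, not how likely a change is. The point is modest, but worth settling before the primary data are analysed.

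**What to change.** - In SAP 7.4, 7.9.1.2 and 7.9.1.6, trigger imputation when more than 5% of PAS subjects lack the endpoint, meaning that either period average is missing. This restores the protocol's unit.
- Bring SAP 7.4 into line with the PAS of SAP 7.1.3 (first 28 randomized), so that randomized subjects without an endpoint are not replaced.
- Keep multiple imputation as the primary handling above the threshold, as both documents have it.
- Add a sensitivity analysis that keeps all 28 in the denominator and counts a missing endpoint as no reduction. It uses the exact test and needs no pooling rule. It also covers a single missing subject (3.6%), who falls below both triggers.
- If the redacted text does not already do so, state the handling below the threshold and the pooling method.

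The cost is a few sentences in the SAP and a little extra analysis. Making missing-as-no-reduction the primary method is not proposed: it would replace what both documents prespecify and would need a protocol change.
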